## 18.1.2. TEAEs Leading to Discontinuation of Study Medication

TEAEs leading to permanent discontinuation of study medication (i.e., monotherapy and/or combination therapy) are those events for which "Action Taken with Study Treatment" is recorded as "Drug withdrawal" on the Adverse Event page of the eCRF. For TEAEs leading to discontinuation of study medication, summaries of incidence rates (frequencies and percentages) by SOC and PT will be prepared.

#### 18.1.3. Serious Adverse Events

Serious adverse events (SAEs) are those events recorded as "Serious" on the Adverse Events page of the (e)CRF. A summary of serious TEAEs by SOC and PT will be prepared.

Page 36 of 46

## 18.1.4. Adverse Events Leading to Death

TEAEs leading to Death are those events which are recorded as "Fatal" for the Outcome field on the Adverse Events page of the (e)CRF. A summary of TEAEs leading to death by SOC and PT will be prepared.

#### 18.2. Deaths

If any patients die (eCRF page: End of Study Treatment) during the study, the information will be presented in a summary table and a data listing using SAF population. If a patient died during Monotherapy (eCRF page: End of Study Treatment, Variable: Reason treatment not completed), then the data will be summarized under Monotherapy, else the summary will be provided under Combination Therapy.

## 18.3. Laboratory Evaluations

Results from the central laboratory will be included in the reporting of this study for Hematology (eCRF page: Local Laboratory Results: Hematology), Serum Chemistry (eCRF page: Local Laboratory Results: Chemistry), Urine Pregnancy Test (eCRF page: Urine Pregnancy Test), and Coagulation (eCRF page: Local Laboratory Results: Coagulation). A list of laboratory assessments to be included in the outputs is included in protocol Section 8.2.3. Presentations will use SI Units.

The following summaries will be provided for laboratory data:

Quantitative data will be summarized using descriptive statistics (mean, SD, median, Q1, Q3, minimum, and maximum) of actual values and changes from baseline for each nominal visit over time. Changes from baseline at each nominal visit over time will also be presented in boxplots. End of Treatment visit will be summarized separately. Qualitative data based on reference ranges will be described according to the categories (i.e. Low, Normal, High).

All lab tests (at screening and any further scheduled control during the study), should be recorded in "lab test pages of the CRF" and only a new and clinically significant (CS) or a CS worsening of lab test after stud drug administration (monotherapy and/or combination therapy), should be recorded in the CRF AE pages.

If both central and local labs are collected for a patient, these summary statistics by visit will be based only on the central lab collected data, while summaries of worst during-treatment abnormalities will be based on both local and central lab data.

- Actual and change from baseline by visit (for quantitative measurements) for Monotherapy and Combination Therapy using SAF population.
- shifts from baseline normal to at least one result above normal
- shifts from baseline normal to at least one result below normal
- A patient may present a lab test change from baseline also after monotherapy. In this case if
  the patient doesn't start the combination phase (for any reason), a clinically significant
  change compared to baseline lab after the monotherapy should also be recorded and
  evaluated.

Page 37 of 46

- All other parameters collected on the eCRF will be listed in dedicated listings presenting all corresponding collected information on the eCRF.
- Urinalysis: all urinalysis parameters
- Pregnancy test
- Listings of laboratory results will be provided for all laboratory parameters. These listings will be sorted by parameters and assessment dates or visits for each patient; laboratory values that are outside the normal range will be flagged along and corresponding normal ranges will be provided.
- In addition, listings of abnormal values will be provided for chemistry, hematology and urinalysis parameters. If there is at least one abnormal result for any parameter, all the data for that parameter will be included in the listing.
- For all tests not mentioned above but present in the clinical data, a listing of patients with at least one result for the relevant test will be provided.

A by-patient listing of all laboratory data and pregnancy test data will be presented for both Monotherapy and Combination therapy using the SAF population.

#### 18.4. ECG Evaluations

The following ECG (eCRF page: 12 Lead ECG) parameters will be reported for this study:

- PR Interval (msec)
- QRS Interval (msec)
- RR Interval (msec)
- QT Interval (msec)
- QTcF Interval (msec) [derived]
- HR (bpm)
- Overall assessment of ECG (Investigator's judgment):
  - Normal
  - o Abnormal, Not Clinically Significant (ANCS)
  - o Abnormal, Clinically Significant (ACS)
  - The 12-lead Electrocardiogram (ECG) assessment will be performed during screening (baseline) and at the Discontinuation / End-of-Treatment visit. For each of the ECG parameters, descriptive statistics at baseline and at the Discontinuation / End-of-Treatment visit and changes from baseline will be summarized by treatment group.
  - The incidence and percentage of patients with the worst potentially clinically significant abnormalities (PCSA) for ECG parameters will be summarized during the on-treatment period. Each patient will be counted only once within each category. As ECG assessments are only performed during screening and at the Discontinuation/End-of-Treatment visit, the denominator to calculate percentages for each PCSA category is the number of patients with Discontinuation/End of Treatment visit.

Test Potentially Clinically Significant Abnormalities (PCSA) Criteria

Page 38 of 46

Heart Rate	$\leq$ 50 bpm and decrease from baseline $\geq$ 20 bpm
	$\geq$ 120 bpm and increase from baseline $\geq$ 20 bpm
PR Interval	$\geq$ 220 ms and increase from baseline $\geq$ 20 ms
QRS	≥ 120 ms
QTcF and QTcB absolute	>450 ms
	>480 ms
	>500 ms
QTcF and QTcB change	Increase from baseline > 30 ms
from baseline	Increase from baseline > 60 ms
0	

QTc will be corrected based on Fridericia's formula for QTcF and Bazett's formula for QTcB (QTcF= QT/ $\sqrt[3]{RR}$  and QTcB= QT/ $\sqrt{RR}$ ) where RR=60/heart rate. Baseline QTcF and QTcB will be derived from the visit that ECG parameters are flagged as baseline.

	1 28	
QT Scale	Male (msec)	Female (msec)
Very Short QT	330	340
Short QT	360	370
Normal QT	390	400
Long QT	450	460
Very Long QT	470	480

A QTc interval of at least 480 milliseconds is a predictor for increased risk for symptoms, whereas a QTc of at least 00 milliseconds predicts an increased risk of life-threatening cardiac events.

A categorical summary of QTcF interval and QT interval corrected by Bazett's formula (QTcB) will be provided using counts and percentages at Baseline and maximum postbaseline by treatment for the following categories:

- Result ≤450 msec;
- Result >450 and  $\leq 480$  msec;
- Result >480 and  $\leq 500$  msec;
- Result >500 msec;
- Change from Baseline ≤30 msec;
- Change from Baseline >30 and ≤60 msec;
- Change from Baseline >60 msec.

The following summaries will be provided for ECG data:

- Actual and change from baseline by visit (for quantitative measurements).
- Shift from baseline of ECG Interpretation Results.

ECG parameters recorded in eCRF form "12 Lead ECG", will be summarized using the SAF population for the monotherapy and Combination therapy. All ECG data will be listed for both Monotherapy and Combination Therapy using the SAF population.

A listing of abnormal 12-lead ECGs will be provided with all relevant information and derived variables.

Page 39 of 46

Unscheduled ECG measurements will not be used in computing the descriptive statistics for change from baseline at each post-baseline time point. However, they will be used in the analysis of notable ECG changes.

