- 11. Patients with sick sinus syndrome, including sino-atrial block.
- 12. Patient with second- and third-degree heart block (without a pacemaker).
- 13. History of bronchospasm and bronchial asthma.
- 14. Untreated phaeochromocytoma.
- 15. Patients with bradycardia (heart rate < 60 bpm; < 50 bpm in patients already on BBs treatment).
- 16. Patient with history of metabolic acidosis.
- 17. Patients with severe peripheral circulatory disturbances.
- 18. Participation in another interventional study within the last 30 days before Screening Visit (Visit 1).
- 19. Patients with diseases that, in the opinion of the Investigator, prevent a careful adherence to the protocol.
- 20. Patients using and not suitable for withdrawing the prohibited medications prior to the administration of study treatment.
- 21. Pregnant and breastfeeding women. NOTE: a pregnancy test will be performed on all women of childbearing potential at each study visit.
- 22. Patients with medical history of cirrhosis (Child Pugh class B or higher).
- 23. History of unexplained syncope within the prior 2 years, or a known syncopal disorder.
- 24. Patients who received renal denervation in the last 3 years or other device-based non-pharmacological treatment of hypertension.
- 25. Any other contraindication to either NEB or RAM as per respective SmPC.

MENARINI	Global Medical Department Protocol Template		
Identification Number	Version Number	State	Effective date
FORM-000050125	3.0, CURRENT	Effective	13 May, 2022

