A single 12-lead resting ECG will be recorded after the patient has been in supine position for at least 5 minutes to calculate the heart rate and measure PR, QRS, QT, and QTc intervals at Visit 1 (Week -4) and Visit 5 (Week 12). The results will be recorded in the eCRF. A trained clinical site physician will perform the clinical assessment of each 12-lead ECG. Additional 12-lead ECGs will be performed if judged to be clinically appropriate or if the ongoing review of the data suggests a more detailed assessment of ECGs is required.

Urine Pregnancy tests

Urine pregnancy tests (only for female of child-bearing potential) will be performed at each Visit 1, 2, 3, 4, and 5, by determination of the urine β human chorionic gonadotropin, using locally available commercial dipsticks. Unscheduled re-tests can be performed as required according to the Investigator's judgment.

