Study assessment and procedures	The Screening Visit is a mandatory in-clinic visit and therefore should be performed at the site. The Principal Investigator continues to be responsible for reviewing all study-related assessments. The participant may not be able to reach the site to perform blood pressure (BP) measurement for primary and secondary analysis, clinical laboratory tests, vital sign and physical examination, electrocardiogram, or other assessments required by the study flow chart. In such cases, these assessments will be performed by the health care professionals (study staff or qualified designee) at participant's home, if allowed per country regulations. If home visits are restricted, the assessments can be performed by phone or video (telemedicine facilities). The participants will be provided with blood pressure measurement device for measuring BP and the BP will be measured by the participant with guidance from Investigator via telemedicine. For clinical laboratory tests and ECG (except Screening Visit) authorized/certified (as legally required nationally) local facilities can also be used. In such cases, the End of Assessment/Early Withdrawal visits should be prioritized, and attempts should be made to complete the assessments. At a minimum, the blood pressure monitoring (either by site staff or participant, as applicable), study medication accountability, assessment of AEs and concomitant medications should be performed.
Remote Monitoring Visit	Study monitors may consider ongoing remote data review and remote data verification, where applicable and if site agreed with this approach, and if

RENARIN	Global Medical Department		
Protocol Template			
Identification Number	Version Number	State	Effective date
FORM-000050125	3.0, CURRENT	Effective	13 May, 2022

	allowed per local regulations, to confirm that data entered into the eCRF by authorized study center personnel are accurate, complete, and wherever
	possible verifiable from source documents; that the safety and rights of
	participants are being protected; and that the study is being conducted in
	accordance with the currently approved protocol and any other study
	agreements, ICH GCP, and all applicable regulatory requirements. The
	procedures for remote data review must be detailed in the monitoring plan.
Data Quality Assurance	During the period of travel restrictions or social distancing, the Sponsor
	may implement remote monitoring in place of on-site visits where available

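### SAP 18.4: the on-treatment ECG abnormality table sets no baseline condition for QRS and absolute QTc, so it can overstate new abnormalities, chiefly for QRS

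*SAP*

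**What the plan says.** SAP 18.4 introduces the table of potentially clinically significant abnormalities (PCSA) with: "The incidence and percentage of patients with the worst potentially clinically significant abnormalities (PCSA) for ECG parameters will be summarized during the on-treatment period". Its criteria follow two patterns.

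- **Limit plus change from baseline:** heart rate (50 bpm or less with a fall of at least 20, or 120 bpm or more with a rise of at least 20) and PR (220 ms or more with a rise of at least 20 ms).
- **Limit only:** QRS (120 ms or more) and the rows headed "QTcF and QTcB absolute" (above 450, 480 and 500 ms).

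QTc increases are separate rows, "Increase from baseline > 30 ms" and the same for 60 ms. They are not combined with the absolute rows.

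On percentages, SAP 18.4 says "the denominator to calculate percentages for each PCSA category is the number of patients with Discontinuation/End of Treatment visit", because ECGs are done only at screening and at that visit. Later in the section, unscheduled ECGs are kept out of the by-visit change summaries, but: "However, they will be used in the analysis of notable ECG changes". Protocol 8.2 foresees such recordings: "Additional 12-lead ECGs will be performed if judged to be clinically appropriate".

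SAP 18.4 also plans QTcF/QTcB categories at baseline and at the post-baseline maximum, actual values and changes for ECG parameters, a shift table of the ECG interpretation, and listings. Protocol 12.5 promises shift tables for each ECG parameter in three investigator-judged classes: normal, abnormal not clinically significant, abnormal clinically significant.

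**The concern.** A table labelled as incidence during treatment should count what arose or worsened during treatment. Two sets of rows here count whoever is beyond the limit on treatment, including patients who were beyond it before the first dose.

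This does not fit the plan's own definitions elsewhere. The secondary safety endpoint (Protocol 4, SAP 2.2) concerns abnormal change in ECG parameters. Laboratory shifts (SAP 18.3) start from a normal baseline. Treatment-emergent adverse events (SAP 18.1) must be new or worsened.

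The eligibility criteria do not close the gap. They set no QRS or QTc limit and do not name bundle branch block. Higher-degree block is excluded only in part, "Patient with second- and third-degree heart block (without a pacemaker"), so this criterion does not bar a paced patient. With no control arm there is no background rate to compare against, and pre-existing conduction findings could be read as arising on a regimen in which every patient takes a beta-blocker.

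**Working it through.** SAP 18.4 states no ECG rate or count, so there is no planned figure to reproduce. The check has three parts.

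**1. One patient through the definitions.** Take a patient with identical ECG values at Visit 1 and Visit 5.

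| Row | Baseline condition | Patient already beyond the limit at Visit 1, unchanged |
|---|---|---|
| Heart rate | change of at least 20 bpm | not counted |
| PR | rise of at least 20 ms | not counted |
| QRS | none | counted |
| QTc absolute | none | counted |
| QTc change | rise above 30 or 60 ms | not counted |

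**2. Possible size.** Inputs:

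- N = 215, the completer target in Protocol 12.2, borrowed as the number with an end-of-treatment ECG.
- b = share beyond the limit at Visit 1 (assumption).
- p = share of those still beyond it on treatment (assumption).
- i = new cases among patients below the limit at Visit 1 (assumption).

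Percentage shown = b × p + (1 − b) × i.

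With i = 0 and p = 1:

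- b = 2%: 0.02 × 215 = 4.3, about 4 patients; 4/215 = 1.9%.
- b = 10%: 0.10 × 215 = 21.5, about 22 patients; 22/215 = 10.2%.
- New cases: 0/215, exact 95% upper limit 1.7%.

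With i = 1% the new-case rate among patients below the limit at Visit 1 stays 1.00%. The table would show:

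| b | p = 1 | p = 0.8 | Share of counted cases that are pre-existing (p = 1) |
|---|---|---|---|
| 0% | 1.00% | 1.00% | 0% |
| 1% | 1.99% | 1.79% | 50% |
| 3% | 3.97% | 3.37% | 76% |
| 5% | 5.95% | 4.95% | 84% |
| 10% | 10.90% | 8.90% | 92% |

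For example, at b = 5% and p = 1: 0.05 + 0.95 × 0.01 = 0.0595, and 0.05/0.0595 = 84%.

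**3. Denominator.** The stated reason, that ECGs exist only at screening and the final visit, conflicts with Protocol 8.2 and with the later sentence on unscheduled ECGs in SAP 18.4. Two mismatches can follow:

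- A patient whose abnormality appears only on an unscheduled ECG, and who has no final visit, is in the numerator only.
- A patient with a final visit but no post-baseline ECG is in the denominator only. Under COVID-19 restrictions the minimum set in Protocol Appendix 2 is BP monitoring plus "study medication accountability, assessment of AEs and concomitant medications should be performed"; the ECG is not in it.

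Illustration (all counts assumed): 3 cases with a final visit and 2 without give 5/215 = 2.33% under the SAP rule. If 5 to 20 patients have a post-baseline ECG but no final visit, a matched denominator gives 5/220 = 2.27% to 5/235 = 2.13%.

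**The case against.** The strongest reply is that the number of patients beyond an absolute limit on treatment is a legitimate descriptive count, and that the plan offers other ways to see baseline status.

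- **QTc.** The baseline and maximum post-baseline categories show the pre-existing burden, and an unchanged long QTc cannot trigger the change rows. This stands at group level. The two distributions are not cross-classified by patient, but QTc is much less exposed than QRS.
- **QRS.** The per-parameter shift tables in Protocol 12.5 cross-classify each patient by baseline, and the listings allow individual checking. A reader might infer that the PCSA table is the only categorical conduction output; these shift tables show that it is not. However, they use the investigator's judgement rather than the 120 ms limit, and SAP 18.4 itself names only the ECG interpretation. The table shells are separate documents, so absence can be asserted only of the SAP text.
- **Eligibility.** Exclusions for serious cardiovascular disease, symptomatic coronary disease, severe heart failure, sick sinus syndrome and labelled contraindications will remove some patients with conduction abnormalities. How many would remain is unknown, and the 2-10% range is not drawn from the documents.
- **Denominator.** The mismatch requires the undefined notable ECG changes to include the PCSA table, and patients of the kind described to exist. Early leavers are asked to complete all Visit 5 assessments. Appendix 2 prioritises final visits and lets ECGs be done at local facilities. The effect is probably negligible.

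**Conclusion.** The point holds as one of definition. The QRS and absolute QTc rows measure on-treatment prevalence under a label of incidence, so they can overstate new abnormalities. The direction is upward wherever pre-existing abnormalities persist, and there is no effect if nobody is beyond the limit at Visit 1. The figures of 4-22 of 215 (1.9-10.2%) rest on an assumed 2-10% baseline prevalence, full persistence, no new case and 215 evaluable ECGs. They show what the rule permits and do not predict the result.

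A reader might go further and conclude that the trial's ECG abnormality rates are wrong. The documents do not support that: they report no rates, and the counts would be valid as prevalence. Nor do they support treating the denominator as a material source of error. It is an internal inconsistency with a small conditional effect. The matter is confined to a descriptive safety table.

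**What to change.** In SAP 18.4:

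1. **Baseline status.** Present QRS of 120 ms or more and each absolute QTcF/QTcB limit by Visit 1 status. Count as on-treatment incidence only patients who did not meet that limit at Visit 1. Show patients already beyond it on a separate row.
2. **Denominator (minor consistency correction).** State that unscheduled ECGs count towards PCSA. Replace the final-visit denominator, per parameter, with patients who have at least one post-baseline ECG value, and a Visit 1 value where baseline status or change is needed.

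The cost is a few sentences and one table shell. No new data are needed. SAP 4 ties shell changes to a SAP amendment, so both changes should go into one amendment before database lock.

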6.2.2 Exclusion Criteria

Any patient who meets any of the following criteria will not qualify for entry into the study:

- 1. Patients with documented history of hypersensitivity to NEB, RAM, other BBs or other ACE-is, or any related products, excipients of the formulations, as outlined in the relevant Investigator's Brochure (IB), summary of product characteristics (SmPC) or local package inserts for Nebivolol and Ramipril.
- 2. Patients with serious disorders (in the opinion of the Investigator) which may limit the ability to evaluate the efficacy or safety of the tested medications, including cerebrovascular, cardiovascular, renal, respiratory, hepatic, gastrointestinal, endocrine, or metabolic, hematological, or oncological, neurological, and psychiatric diseases. The same applies for immunocompromised and/or neutropenic patients.
- 3. Patients having a history of the following conditions within the last 6 months: myocardial infarction, unstable angina pectoris, percutaneous coronary intervention, bypass surgery, heart failure, hypertensive encephalopathy, valve replacement

RENARIN	Glot	oal Medical Department	
	Protocol Template		
Identification Number	Version Number	State	Effective date
FORM-000050125	3.0, CURRENT	Effective	13 May, 2022

(transcatheter aortic valve implantation, mitraclip), cerebrovascular accident (stroke), or transient ischemic attack.

- 4. Patients with condition of hypotension with SBP < 90 mmHg and/or DBP < 60 mmHg.
- 5. Acute heart failure (12 months before enrolment), cardiogenic shock, or episodes of heart failure decompensation requiring intravenous inotropic therapy.
- 6. Patients with secondary hypertension of any etiology including renal diseases, Cushing's syndrome, hyperaldosteronism, renovascular disease and thyroid disorders.
- 7. Patients with severe heart failure (New York Heart Association classification III-IV) a narrowing of the aortic or bicuspid valve, an obstruction of cardiac outflow (obstructive, hypertrophic cardiomyopathy), obstruction of the outflow tract of the left ventricle (e.g., high grade aortic stenosis) or symptomatic coronary disease.
- 8. Patients with clinical evidence of renal disease (including significant bilateral renal artery stenosis or renal artery stenosis in a single functioning kidney), severe renal impairment or renal transplant.
- 9. Patients with clinically relevant hepatic impairment.
- 10. Patients with a history of angioneurotic edema.

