## 18.5. Vital Signs

The following Vital Signs (eCRF page: Vital Signs) measurements will be reported for this study:

- Sitting Systolic Blood Pressure (mmHg)
- Sitting Diastolic Blood Pressure (mmHg)
- Pulse Rate (bpm)
- Respiratory Rate (breaths/min)
- Body Temperature ( C)
- All vital sign parameters will be summarized using descriptive statistics (mean, SD, median, Q1, Q3, minimum, and maximum) of actual values and changes from baseline for each planned visit over time. Discontinuation/End of Treatment visit will be summarized separately. The changes computed will be the differences from baseline.
- The maximum on-treatment change from baseline will be calculated and categorized by vital sign measurement. Missing values will define a separate category. A summary of maximum shift from baseline by category will be provided by treatment arm.

• Categories of Change from Baseline for Vital Sign Parameters

Parameters	Categories of Change from Baseline
Body temperature increase	• $< 1  \dot{C}, 1 - < 2  \dot{C}, 2 - < 3  \dot{C}, \ge 3  \dot{C}$
Weight increase	<10%, ≥ 10%
Weight decrease	<10%, ≥ 10%
Heart rate increase from baseline  • <100 bpm ; ≥ 100 bpm	• ≤20 bpm, >20 – 40 bpm, >40 bpm
Heart rate decrease from baseline  • <100 bpm ; ≥ 100 bpm	• ≤20 bpm, >20 – 40 bpm, >40 bpm
SBP increase from baseline  • <130 mmHg; ≥ 130 mmHg for age <65	• ≤20 mmHg, >20 – 40 mmHg, >40 mmHg
SBP decrease from baseline  • <130 mmHg; ≥ 130 mmHg, for age <65	• ≤20 mmHg, >20 – 40 mmHg, >40 mmHg
SBP increase from baseline  • <140 mmHg; ≥ 140 mmHg for age ≥65	• ≤20 mmHg, >20 – 40 mmHg, >40 mmHg
SBP decrease from baseline  • <140 mmHg; ≥ 140 mmHg, for age ≥65	• ≤20 mmHg, >20 – 40 mmHg, >40 mmHg
DBP increase from baseline  • <80 mmHg; ≥ 80 mmHg	• ≤20 mmHg, >20 – 40 mmHg, >40 mmHg
DBP decrease from baseline  • <80 mmHg; ≥ 80 mmHg,	• ≤20 mmHg, >20 – 40 mmHg, >40 mmHg

Page 40 of 46

Respiration rate increase from baseline <20 • breaths/min; ≥ 20 breaths/min	• ≤5 breaths/min, >5 – 10 breaths/min, >10 breaths/min
Respiration rate decrease from baseline <20 • breaths/min; ≥ 20 breaths/min	• ≤5 breaths/min, >5 – 10 breaths/min, >10 breaths/min

• bpm = beats per minute; DBP=diastolic blood pressure; SBP=systolic blood pressure, min=minute.

The following summaries will be provided for vital signs data:

• Actual and change from baseline by visit for Monotherapy and Combination therapy using the SAF population.

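### The SAP's only low heart-rate criterion is insensitive in patients already on a beta-blocker at Visit 1, and no table described in its text counts patients by low pulse or low BP

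*SAP*

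**What the plan says.** The safety endpoint (Protocol section 4; SAP 2.2) includes clinically significant abnormal change in vital signs and ECG.

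**ECG.** The table of potentially clinically significant abnormalities (PCSA) in SAP 18.4 has one low heart-rate row: at or below "50 bpm and decrease from baseline" of at least 20 bpm. Both conditions are required. The QRS and absolute QTc rows in the same table use a value alone. On timing, SAP 18.4 says: "As ECG assessments are only performed during screening and at the Discontinuation/End-of-Treatment visit". Baseline is therefore Visit 1.

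**Vital signs.** SAP 18.5 states: "The maximum on-treatment change from baseline will be calculated and categorized by vital sign measurement". The rows concerned are:
- "Heart rate decrease from baseline", split at 100 bpm
- "SBP decrease from baseline", split at 130 mmHg under age 65 and at 140 mmHg from age 65
- "DBP decrease from baseline", split at 80 mmHg

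Each is banded as a change of up to 20, more than 20 to 40, or more than 40. SAP 18.5 also gives descriptive statistics of actual values by visit, including the minimum, and a by-patient listing.

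**Limits stated elsewhere.** Protocol 6.2.2, exclusion 4: "Patients with condition of hypotension with SBP < 90 mmHg and/or DBP < 60 mmHg". Exclusion 15: "Patients with bradycardia (heart rate < 60 bpm; < 50 bpm in patients already on BBs treatment".

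**The concern.** Low heart rate and low BP are the foreseeable haemodynamic effects of combining a beta-blocker with an ACE inhibitor and up-titrating. A reader will look to the categorical safety tables for how many patients reached a low value.

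The ECG rule asks for a fall of 20 bpm from a baseline that, in about half the patients, is already lowered by treatment. Those patients have little room to fall that far, so the row can look reassuring where low rates are likeliest. The vital-sign table cannot make up for this. It grades the size of the fall, which for BP is the intended effect, and has no low-value row.

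The endpoint also lacks a matching output. Protocol 12.5 gives shift tables of clinically significant values for ECG and physical examination only, and SAP 18.5 neither defines nor counts a clinically significant vital sign.

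**Working it through.** The documents state no figure for this point, so there is none to reproduce. Steps 1 and 2 follow from the text alone; step 3 needs assumptions.

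**1. ECG rule.** Inputs: the joint rule in SAP 18.4, and entry allowed from 50 bpm on a beta-blocker (exclusion 15). With baseline *b* and final rate *h*, the row counts a patient only if *h* ≤ 50 and *b* − *h* ≥ 20, that is *h* ≤ min(50, *b* − 20).

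| Baseline (bpm) | Final rate needed to count |
|---|---|
| 70 | ≤ 50 |
| 65 | ≤ 45 |
| 62 | ≤ 42 |
| 59 | ≤ 39 |
| 50 | ≤ 30 |

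**2. Vital-sign cells.** The SAP does not say whether the split applies to the baseline or the on-treatment value. These pairs share a cell either way.

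| Measure | Patient A | Patient B | Shared band | Side of split |
|---|---|---|---|---|
| Pulse | 58 to 42 (fall 16) | 80 to 75 (fall 5) | ≤ 20 | all below 100 |
| SBP, age < 65 | 132 to 88 (fall 44) | 165 to 122 (fall 43) | > 40 | both baselines ≥ 130, both final values < 130 |
| DBP | 80 to 58 (fall 22) | 100 to 78 (fall 22) | > 20 to 40 | both baselines ≥ 80, both final values < 80 |

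In the BP rows, patient A is below the exclusion 4 limit and patient B is a good responder.

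**3. Share missed by the ECG rule (assumed heart rates).** The documents give no heart-rate distribution. Baseline and final rates were simulated as bivariate normal, with SD 8 to 10 and correlation 0.5 to 0.7. Captured share = P(*h* ≤ 50 and fall ≥ 20) / P(*h* ≤ 50).

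| Group at Visit 1 | Assumed baseline mean and floor | Assumed mean fall | Captured | Missed |
|---|---|---|---|---|
| Beta-blocker | 60 to 75, floor 50 | 0 to 3 | 1% to 34% | 66% to 99% |
| ACE inhibitor | 70 to 80, floor 60 | 6 to 12 | 17% to 74% | 26% to 83% |

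A narrower set of assumptions for the beta-blocked group (mean 63, SD 7, floor 50; mean fall 2 to 4, SD 7) has 11% to 16% ending at or below 50 bpm, with 4% to 6% of those flagged.

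The number of patients is less certain than the share. Take the cap of 110 per drug (Protocol section 5) and suppose every patient has a final ECG:
- Baseline mean 60, SD 8, mean fall 3, correlation 0.5: 0.1548 × 110 = 17.0 patients end at or below 50 bpm, and 0.0123 × 110 = 1.4 are flagged.
- Baseline mean 75: between 0.0007 × 110 = 0.1 and 0.0129 × 110 = 1.4 patients reach 50 bpm or less, so little could be missed.

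**The case against.** The strongest reply is that low values do not vanish:
- Bradycardia or hypotension reported as an adverse event is counted by preferred term (SAP 18.1.1).
- A physician assesses each ECG, the interpretation is tabulated as a shift from baseline, and abnormal ECGs are listed (SAP 18.4).
- Minima of actual pulse and BP appear by visit, and every reading is listed (SAP 18.5).
- A newly developed exclusion criterion can lead to withdrawal (Protocol section 10), and withdrawal reasons are tabulated (SAP 9.1).

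This stands, and it rules out the inference that bradycardia and hypotension go uncounted altogether. It does not supply the missing count. A minimum is one value per visit, not a number of patients. SAP 6.3 leaves unscheduled readings out of by-visit summaries. Adverse-event tables depend on reporting, and Protocol 9.9 says when a laboratory abnormality becomes an adverse event but gives no such rule for pulse or BP. Scheduled ECGs occur only at Visits 1 and 5, so a low rate in between is seen through pulse.

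Other fair points:
- The endpoint speaks of change, and a value-plus-change rule fits that; the PR row has the same form. This supports keeping the row, not relying on it alone.
- From a baseline SBP of at least 130, any value below 90 is a fall of more than 40, the top band. From a baseline DBP of at least 80, any value below 60 is a fall of more than 20. Such patients are not hidden among small changes, but they cannot be told from large responders.
- Not every pair shares a cell. Under age 65, SBP 165 to 138 and 112 to 88 share a band but fall on different sides of the 130 split.
- Exclusions 4 and 15 are written as entry limits, not on-treatment safety limits.
- The table shells are a separate document and were not available, so the point is limited to tables described in the SAP text.

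**Conclusion.** The point holds in a limited form. By arithmetic, the ECG low-rate row is insensitive in patients beta-blocked at Visit 1. By the text, SAP 18.5 has no row that counts patients by low pulse, SBP or DBP. Detection then rests on adverse-event reporting, ECG interpretation, minima and listings.

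Three stronger readings are not supported:
- The ECG rule does not count falls in place of low values. It requires both; the change-only description fits SAP 18.5.
- The rule cannot be said to miss most low rates in all patients. For those on an ACE inhibitor at Visit 1, whose baseline ECG precedes nebivolol, the illustrative range is 26% to 83% missed. Only in the beta-blocked half does it stay above one half, at 66% to 99%.
- No particular number of missed patients can be claimed, because the heart-rate distribution is assumed.

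No efficacy result or sample-size figure is affected.

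**What to change.** **SAP 18.5.** Add the number and percentage of patients with any post-baseline SBP < 90 and/or DBP < 60 mmHg, and with low pulse, by visit and by Monotherapy/Combination period. State that unscheduled readings are included, as an exception to SAP 6.3. For pulse, use both limits in exclusion 15: < 50 bpm on a beta-blocker and < 60 bpm otherwise. A single limit of 50 for everyone would not be the protocol's limit for ramipril monotherapy. Label all of these as reporting thresholds, not management rules.

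**SAP 18.4.** Tabulate ECG heart rate ≤ 50 bpm without the fall condition, beside the existing PCSA row and split by beta-blocker use at Visit 1.

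**Cost.** A few table rows from pulse and BP already recorded at every visit, and from ECGs already planned. SAP section 4 does not allow the shells to change without a SAP amendment, so one is needed. Some flagged values will be symptom-free and need a line of interpretation.
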